#### 11.1.5 Duration of Response

Duration of overall response: The duration of overall response is measured from the time measurement criteria are met for CR or PR (whichever is first recorded) until the first date that recurrent or progressive disease is objectively documented (taking as reference for progressive disease the smallest measurements recorded since the treatment started).

The duration of overall CR is measured from the time measurement criteria are first met for CR until the first date that recurrent disease is objectively documented.

Duration of stable disease: Stable disease is measured from the start of the treatment until the criteria for progression are met, taking as reference the smallest measurements recorded since the treatment started.

#### 11.1.6 Progression-Free Survival

PFS is defined as the duration of time from start of treatment to time of progression.

### 11.2 Other Response Parameters

Pathologic complete response will be assessed on surgical specimens. This will include an evaluation of evidence of residual gross and microscopic disease in the resected rectum and

lymph nodes.

## **12. DATA REPORTING / REGULATORY REQUIREMENTS**

Adverse event lists, guidelines, and instructions for AE reporting can be found in Section 7.0 (Adverse Events: List and Reporting Requirements).

### **12.1 Data Reporting**

#### 12.1.1 Method

This study will be monitored by the Clinical Data Update System (CDUS) version 3.0. Cumulative CDUS data will be submitted quarterly to CTEP by electronic means. Reports are due January 31, April 30, July 31 and October 31. Instructions for submitting data using the CDUS can be found on the CTEP web site (<http://ctep.cancer.gov/reporting/cdus.html>).

**Note:** All adverse events that have occurred on the study, including those reported through AdEERS, must be reported via the monitoring method identified above.

#### 12.1.2 Responsibility for Data Submission

*N/A*

### **12.2 Cooperative Research and Development Agreement (CRADA)/Clinical Trials Agreement (CTA)**

The agent(s) supplied by CTEP, DCTD, NCI used in this protocol is provided to the NCI under a Collaborative Agreement (CRADA, CTA, CSA) between the Pharmaceutical Company(ies) (hereinafter referred to as “Collaborator(s)”) and the NCI Division of Cancer Treatment and Diagnosis. Therefore, the following obligations/guidelines, in addition to the provisions in the “Intellectual Property Option to Collaborator” (<http://ctep.cancer.gov/industry>) contained within the terms of award, apply to the use of the Agent(s) in this study:

1. Agent(s) may not be used for any purpose outside the scope of this protocol, nor can Agent(s) be transferred or licensed to any party not participating in the clinical study. Collaborator(s) data for Agent(s) are confidential and proprietary to Collaborator(s) and shall be maintained as such by the investigators. The protocol documents for studies utilizing investigational Agents contain confidential information and should not be shared or distributed without the permission of the NCI. If a copy of this protocol is requested by a patient or patient’s family member participating on the study, the individual should sign a confidentiality agreement. A suitable model agreement can be downloaded from: <http://ctep.cancer.gov>.
2. For a clinical protocol where there is an investigational Agent used in combination with (an)other investigational Agent(s), each the subject of different collaborative agreements, the access to and use of data by each Collaborator shall be as follows (data pertaining to such combination use shall hereinafter be

referred to as "Multi-Party Data.”):

- a. NCI will provide all Collaborators with prior written notice regarding the existence and nature of any agreements governing their collaboration with NIH, the design of the proposed combination protocol, and the existence of any obligations that would tend to restrict NCI's participation in the proposed combination protocol.
  - b. Each Collaborator shall agree to permit use of the Multi-Party Data from the clinical trial by any other Collaborator solely to the extent necessary to allow said other Collaborator to develop, obtain regulatory approval or commercialize its own investigational Agent.
  - c. Any Collaborator having the right to use the Multi-Party Data from these trials must agree in writing prior to the commencement of the trials that it will use the Multi-Party Data solely for development, regulatory approval, and commercialization of its own investigational Agent.
3. Clinical Trial Data and Results and Raw Data developed under a Collaborative Agreement will be made available exclusively to Collaborator(s), the NCI, and the FDA, as appropriate and unless additional disclosure is required by law or court order. Additionally, all Clinical Data and Results and Raw Data will be collected, used, and disclosed consistent with all applicable federal statutes and regulations for the protection of human subjects including, if applicable, the *Standards for Privacy of Individually Identifiable Health Information* set forth in 45 C.F.R. Part 164.
  4. When a Collaborator wishes to initiate a data request, the request should first be sent to the NCI, who will then notify the appropriate investigators (Group Chair for Cooperative Group studies, or PI for other studies) of Collaborator's wish to contact them.
  5. Any data provided to Collaborator(s) for Phase 3 studies must be in accordance with the guidelines and policies of the responsible Data Monitoring Committee (DMC), if there is a DMC for this clinical trial.
  6. Any manuscripts reporting the results of this clinical trial must be provided to CTEP by the Group office for Cooperative Group studies or by the principal investigator for non-Cooperative Group studies for immediate delivery to Collaborator(s) for advisory review and comment prior to submission for publication. Collaborator(s) will have 30 days from the date of receipt for review. Collaborator shall have the right to request that publication be delayed for up to an additional 30 days in order to ensure that Collaborator's confidential and proprietary data, in addition to Collaborator(s)'s intellectual property rights, are protected. Copies of abstracts must be provided to CTEP for forwarding to Collaborator(s) for courtesy review as soon as possible and preferably at least

three (3) days prior to submission, but in any case, prior to presentation at the meeting or publication in the proceedings. Press releases and other media presentations must also be forwarded to CTEP prior to release. Copies of any manuscript, abstract and/or press release/ media presentation should be sent to:

Regulatory Affairs Branch, CTEP, DCTD, NCI  

### 13. STATISTICAL CONSIDERATIONS

#### 13.1 Study Design/Endpoints

This is a Phase I trial in which patients will be treated with escalating doses of AZD6244. There will be no inpatient dose escalation. The primary endpoints will be the MTD and the DLT's. The dose-escalation will proceed in cohorts of 3-6 patients at each dose level. If 0/3 experience DLT, the next cohort starts one dose level higher. If 1/3 experience DLT, up to 3 more patients are started at that same dose level. If 2 or more experience DLT, no further patients are started at that dose. In the event that 2 or more patients of the first three enrolled at dose level 1 develop a DLT, de-escalation to dose level -1 will occur. The MTD or recommended Phase II dose is the dose level at which no more than 1 of 6 patients experience DLT during treatment and the three weeks after completion. Six additional patients will be treated at the recommended phase II dose in order to refine toxicity assessment and obtain reasonable amounts of biologic data.

The dose escalation will proceed only for AZD6244 while capecitabine and radiation doses remain constant. The schema for escalation is as follows:

Dose Escalation Schedule			
Dose Level	Dose		
	AZD6244	Capecitabine	Radiation*
Level -1	50 mg PO QD Weeks 1-7	825 mg/m  PO every 12 hours Weeks 2-7	5040 cGy Weeks 2-7
Level 1	50 mg PO BID Weeks 1-7	825 mg/m  PO every 12 hours Weeks 2-7	5040 cGy Weeks 2-7
Level 2	75 mg PO BID Weeks 1-7	825 mg/m  PO every 12 hours	5040 cGy Weeks 2-7

		Weeks 2-7	
* An additional 360 cGy may be delivered for fixed T4 tumors for a total dose of 5400 cGy			

Toxicity will be scored according to the CTCAE v4.0  
([http://ctep.cancer.gov/protocolDevelopment/electronic\\_applications/docs/ctcae4.pdf](http://ctep.cancer.gov/protocolDevelopment/electronic_applications/docs/ctcae4.pdf)).

Dose-limiting toxicities will be defined as follows (during treatment and within the first three weeks after treatment)

1. Recurring and persistent Grade 3 diarrhea despite appropriate medical therapy.
2. ANC <500 for more than 5 days or neutropenic fever
3. Grade 4 thrombocytopenia
4. Recurring and persistent Grade 3 nausea/vomiting despite appropriate anti-emetic therapy
5. Grade 4 dermatitis acneiform rash
6. Grade 4 fatigue
7. All other non-hematologic toxicities of grade 3 or higher except electrolyte abnormalities that are correctable
8. Delays in radiation treatment due to toxicity of more than 2 weeks (cumulative duration over the course of the entire treatment).

Toxicities should be attributable (possible, probable or definite) to the AZD6244, Capecitabine, and RT to constitute DLT. Patients who develop a DLT will continue Capecitabine and radiation after resolution or partial resolution of the DLT as clinically appropriate, and dose reduction of AZD6244 will occur as in section 5.1.

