#### 4.2 **Definition of Dose-Limiting Toxicity**

- Dose-limiting toxicities will be defined as follows (during treatment and within the first three weeks after treatment):
  1. Recurring and persistent Grade 3 diarrhea despite appropriate medical therapy.
  2. ANC <500 for more than 5 days or neutropenic fever
  3. Grade 4 thrombocytopenia
  4. Recurring and persistent Grade 3 nausea/vomiting despite appropriate anti-emetic therapy
  5. Grade 4 dermatitis acneiform rash
  6. Grade 4 fatigue
  7. All other non-hematologic toxicities of grade 3 or higher except electrolyte abnormalities that are correctable
  8. Delays in radiation treatment due to toxicity of more than 2 weeks (cumulative duration over the course of the entire treatment).
- Management and dose modifications associated with the above adverse events are outlined in Section 5.

- Dose escalation will proceed within each cohort according to the following scheme. Dose-limiting toxicity (DLT) is defined above.

Number of Patients with DLT at a Given Dose Level	Escalation Decision Rule
0 out of 3	Enter 3 patients at the next dose level.
$\geq 2$	Dose escalation will be stopped. This dose level will be declared the maximally administered dose (highest dose administered). Three (3) additional patients will be entered at the next lowest dose level if only 3 patients were treated previously at that dose. If $\geq 2$ initial patients experience a DLT at dose level 1, de-escalation to dose level -1 will occur.
1 out of 3	Enter at least 3 more patients at this dose level. 
 
• If 0 of these 3 patients experience DLT, proceed to the next dose level.
 
• If 1 or more of this group suffer DLT, then dose escalation is stopped, and this dose is declared the maximally administered dose. Three (3) additional patients will be entered at the next lowest dose level if only 3 patients were treated previously at that dose.
 

$\leq 1$ out of 6 at highest dose level below the maximally administered dose	This is generally the recommended phase 2 dose. At least 6 patients must be entered at the recommended phase 2 dose.

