#### 4.4 Duration of Therapy

Treatment with AZD6244 will continue until the completion of chemoradiotherapy or until one of the following criteria applies:

- Toxicity requiring discontinuation (section 4.2)
- Disease progression,
- Intercurrent illness that prevents further administration of treatment,
- Unacceptable adverse event(s),
- Patient decides to withdraw from the study, or
- General or specific changes in the patient's condition render the patient unacceptable for further treatment in the judgment of the investigator.

In the event of a discontinuation of AZD6244 for a dose limiting toxicity the patient will continue to receive capecitabine and radiotherapy if not already completed.

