## 5.0 DOSING DELAYS/DOSE MODIFICATIONS

### 5.1 AZD6244

AZD6244 dose reductions will occur in the event of a DLT. In the event of a DLT that is an overlapping toxicity with Capecitabine, AZD6244 will be dose reduced. If a Capecitabine associated toxicities occur following discontinuation of AZD6244, Capecitabine dose adjustments will occur as deemed appropriate by the Principal Investigator in conjunction with the participating Medical Oncology Associate Investigator. AZD6244 dose reductions will not occur for established non-DLT Capecitabine toxicities (e.g. Grade 2 hand-foot syndrome).

Dose de-escalation will occur as described in the table below for DLT's and the following overlapping toxicities

- **Grade  $\geq 3$  diarrhea that persists despite appropriate medical management including anti-diarrheal medications**
- **Grade  $\geq 3$  nausea and vomiting that persists despite appropriate medical management including anti-nausea medications**
- **Grade 2 hand foot that persists despite interruption of capecitabine**

Dose De-Escalation Schedule			
Dose Level	Dose		
	AZD6244	Capecitabine	Radiation*
Level -1	50 mg PO QD Weeks 1-7	825 mg/m  PO every 12 hours Weeks 2-7	5040 cGy Weeks 2-7
Level 1	50 mg PO BID Weeks 1-7	825 mg/m  PO every 12 hours Weeks 2-7	5040 cGy Weeks 2-7
Level 2	75 mg PO BID Weeks 1-7	825 mg/m  PO every 12 hours Weeks 2-7	5040 cGy Weeks 2-7
* An additional 360 cGy may be delivered for fixed T4 tumors for a total dose of 5400 cGy			

Diarrhea must be managed symptomatically. IV hydration and use of loperamide, as well as close observation, are recommended for diarrhea if clinically indicated. C If control takes

longer than 2 days, medical evaluation including relevant diagnostic procedures, alternative treatment, and possible investigation of DPD deficiency should be considered. Capecitabine and AZD6244 may be held for up to 72 hours and will not be re-started until diarrhea has resolved to grade  $\leq 1$ . In patients with grade 3 diarrhea evaluation for C. difficile colitis should be considered. Patients with neutropenia and diarrhea should be considered for empiric use of prophylactic antibiotics such as oral quinolones.

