## 5.2 Capecitabine

Capecitabine will be withheld in cases of Grade 3 or greater neutropenia or Grade 2 or greater hand-foot syndrome or mucositis that do not respond to medical management. Capecitabine will be restarted after the symptoms improved to Grade 1. The dose of Capecitabine may be adjusted in the event of recurrent Grade 2 or greater hand-foot syndrome, neutropenia, or other Capecitabine toxicities that have not been attributed to AZD6244.

Summary of management of common Capecitabine toxicities during combined AZD6244 and Capecitabine dosing	
Toxicity	Capecitabine dose modification
Grade 2 hand foot syndrome	Interrupt until $\leq$ grade 1. May then restart capecitabine at full dose. For second occurrence, hold capecitabine until $\leq$ grade 1, then restart capecitabine one dose level lower (75% of starting dose first occurrence, 50% of the starting dose the second occurrence, discontinue the third occurrence).
Grade 3 hand foot syndrome	Interrupt until $\leq$ grade 1. Then restart capecitabine one dose level lower (75% of starting dose first occurrence, 50% of the starting dose the second occurrence, discontinue the third occurrence).
Grade 2 thrombocytopenia	Continue at current dose
Grade 3 thrombocytopenia	Hold until recovery until $\leq$ grade 1 then resume one dose level lower*
Grade 4 thrombocytopenia	Hold until recovery until $\leq$ grade 1 then resume one dose level lower*
Grade 3 neutropenia	Hold until recovery until $\leq$ grade 1 then resume one dose level lower*
Grade 4 neutropenia	Hold until recovery until $\leq$ grade 1 then resume one dose level lower*
$\geq$ Grade 3 febrile neutropenia	Hold until resolution of fever and neutropenia to $\leq$ grade 1. Then resume on dose level lower*
*Dose reductions for capecitabine 1. Starting dose 2. 75% of the starting dose 3. 50% of the starting dose	

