#### 4. Discontinuation of capecitabine.

### 5.3 Radiation

Radiation dose will not be adjusted based on toxicity. Delay in treatment may occur in the event that it is felt to be unsafe to deliver treatments due to the clinical status of the patient. Radiation treatment delays will be minimized as efficacy of radiotherapy is decreased with treatment delay. In the event that radiation is delayed for a toxicity, treatment with AZD6244 and capecitabine will be held until resumption of radiation. AZD6244 and capecitabine dose will be modified as described in section 5.1 and 5.2.

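### For some DLTs, section 13.1 permits a capecitabine restart that sections 5.1 and 5.2 do not allow, and it omits the capecitabine reduction required by the 5.2 table

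*Combined protocol and SAP*

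**What the plan says.** Section 13.1, after the list of DLTs, states: "Patients who develop a DLT will continue Capecitabine and radiation after resolution or partial resolution of the DLT as clinically appropriate". The same sentence ends: "dose reduction of AZD6244 will occur as in section 5.1". It gives no recovery grade, does not mention the capecitabine dose, and does not cite 5.2.

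Section 4.2 carries the same DLT list but points more widely: "Management and dose modifications associated with the above adverse events are outlined in Section 5".

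Section 5.1 says of overlapping toxicity: "In the event of a DLT that is an overlapping toxicity with Capecitabine, AZD6244 will be dose reduced". Its de-escalation table keeps capecitabine at 825 mg/m2 at every level. For diarrhea it sets a firm condition on both drugs, which "will not be re-started until diarrhea has resolved to grade" 1 or less.

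Section 5.2 has a table written for combined AZD6244 and capecitabine dosing. After febrile neutropenia the instruction is "Hold until resolution of fever and neutropenia to" grade 1 or less, then to resume at a lower capecitabine dose. The rows for Grade 3 and 4 neutropenia, Grade 3 and 4 thrombocytopenia and Grade 3 hand-foot syndrome follow the same pattern. The first step down is 75% of the starting dose.

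Section 5.3 adds that when radiation is delayed for toxicity, "treatment with AZD6244 and capecitabine will be held until resumption of radiation", with both drug doses modified under 5.1 and 5.2.

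**The concern.** A toxicity that falls from Grade 4 to Grade 2 has partly resolved. On the words of 13.1, capecitabine may then continue. On the words of 5.1 (diarrhea) or 5.2 (hematologic events and hand-foot syndrome), it may not. Someone working from 13.1 is sent to 5.1 alone and never reaches the capecitabine reductions in 5.2.

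Two patients with the same DLT could therefore restart capecitabine at different recovery grades and doses, depending on which section the treating team follows. That is a safety matter for the patient. It also affects the data: the toxicity profile of the combination is a primary objective (section 1.1), the sample is at most 18 (section 13.2), and toxicity after a DLT would be recorded under capecitabine exposures that differ because of the wording.

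**Working it through.** No sample-size or error-rate figure is involved. The check is to set each DLT item (sections 4.2 and 13.1) beside any capecitabine rule in section 5.

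| DLT item | Capecitabine restart condition in section 5 | Capecitabine reduction required in section 5 |
|---|---|---|
| 1. Persistent Grade 3 diarrhea | Grade 1 or less (5.1) | None in the 5.2 table |
| 2. ANC below 500 for over 5 days, or neutropenic fever | Grade 1 or less, and fever resolved if febrile (5.2) | One level lower (5.2 table) |
| 3. Grade 4 thrombocytopenia | Grade 1 or less (5.2) | One level lower (5.2 table) |
| 4. Persistent Grade 3 nausea/vomiting | None stated | None |
| 5. Grade 4 acneiform rash | None stated | None |
| 6. Grade 4 fatigue | None stated | None |
| 7. Other non-hematologic, Grade 3 or higher | Hand-foot syndrome: grade 1 or less; mucositis: Grade 1 (5.2); otherwise none | Grade 3 hand-foot syndrome: one level lower; otherwise none |
| 8. Radiation delay over 2 weeks | No grade of its own; 5.3 refers to 5.1 and 5.2 | As 5.1 and 5.2 |

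Item 2 is placed in the Grade 4 neutropenia row on the assumption that an ANC below 500 is Grade 4. Appendix F grades it so on the RTOG scale; the CTCAE table that governs DLT grading is not reproduced in the protocol.

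**Restart condition.** Section 13.1 applies one condition, full or partial resolution, to all eight items. Items 1, 2, 3 and part of 7 meet a stricter condition in section 5.

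**Dose.** Items 2, 3 and part of 7 also meet a required capecitabine reduction in the 5.2 table, about which 13.1 says nothing. The first step is 0.75 × 825 = 618.75 mg/m2 per dose. If a reader takes the silence of 13.1 to mean no change, the gap is 825 − 618.75 = 206.25 mg/m2 per dose, or 25%.

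**Worked case.** Take a patient whose Grade 4 thrombocytopenia has recovered to Grade 2. Under 13.1 capecitabine may continue if judged appropriate, AZD6244 is reduced, and no capecitabine dose is given. Under 5.2 capecitabine stays on hold, and on reaching grade 1 or less it resumes at 618.75 mg/m2.

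**Cross-references.** Section 4.2 points to all of section 5, section 5.3 to 5.1 and 5.2, and section 13.1 to 5.1 only. None states which text prevails.

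**The case against.** The best defense is that 13.1 is loose rather than wrong. It is qualified by clinical appropriateness, improvement from Grade 4 to Grade 1 is itself a partial resolution, and section 4.2 sends the reader to the whole of section 5. The AZD6244 reduction in 5.1 and the capecitabine reduction in 5.2 can both apply. The text above the 5.2 table also treats capecitabine adjustment as optional, for recurrent toxicity not attributed to AZD6244, so 5.2 is not uniform either. This shows that a careful reader could reconcile the sections. It does not remove the conflict: a discretionary clause is not the same as a fixed hold, 13.1 does not defer to 5.2, and Grade 4 to Grade 2 is also a partial resolution.

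A reader might infer more than the documents support:

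- **That the MTD count is affected.** The 13.1 sentence covers patients who have already had a DLT. Each is already counted, so a later restart, recurrence or radiation delay cannot change that patient's contribution. For diarrhea that is not yet a DLT, the 5.1 rule governs.
- **That every DLT is affected.** Items 4, 5, 6 and most of 7 have no capecitabine restart grade to contradict.
- **That 13.1 fixes capecitabine at full dose.** It is silent on that dose.
- **That 5.1 also lowers capecitabine.** It reduces AZD6244, in agreement with 13.1, and leaves capecitabine changes to discretion once AZD6244 has been discontinued. The required reduction is in the 5.2 table only.
- **That the sections contradict each other on radiation.** Sections 13.1 and 5.3 both rest on clinical judgment. Section 4.4 says that after AZD6244 is stopped for a DLT "the patient will continue to receive capecitabine and radiotherapy if not already completed", which does not rule out an interruption. Section 5.3 adds a condition and keeps the 5.1 and 5.2 modifications.

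**Conclusion.** The point holds for capecitabine after some DLTs. Section 13.1 permits a restart that section 5 does not allow for items 1, 2, 3 and part of 7. For items 2, 3 and part of 7 it also omits a capecitabine reduction that the 5.2 table requires, where the first step is 825 to 618.75 mg/m2 per dose. The 25% gap is a maximum for that step and rests on reading silence as no change.

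The number of patients affected cannot be stated, because the documents give no expected frequency for each type of DLT. The consequence is inconsistent capecitabine restart and exposure after a DLT. It bears on patient safety and on the comparability of toxicity data collected after the event. Dose escalation and the declaration of the MTD are not put in doubt on this ground.

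**What to change.** Reconcile sections 5.1, 5.2 and 13.1. Replace the 13.1 sentence with a reference to all of section 5 (5.1, 5.2 and 5.3), as section 4.2 already does, so that one rule for restart and dose applies after a DLT. In the same edit, bring the 5.2 text and table into line on when capecitabine is reduced.

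Section 5 gives no capecitabine restart condition for items 4, 5, 6 and most of 7. It should therefore say what governs those items once the 13.1 sentence is gone, even if the answer is clinical judgment. The clinical team decides which thresholds and doses apply. No change is needed to how recurring toxicities are scored as DLTs.

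The cost is protocol wording: no added patients, visits or procedures.
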